1.1 PRIMARY OBJECTIVES

- To assess whether it is futile to move deferoxamine mesylate (DFO) into Phase III evaluation as a therapeutic intervention for spontaneous intracerebral hemorrhage (ICH), by comparing the outcome of DFO-treated subjects to placebo-treated subjects with respect to good outcome (defined as modified Rankin Scale [mRS] score of 0-2 at 90 days), in a futility analysis. The futility hypothesis specifies that if the difference in good outcome proportions is less than 12% in favor of DFO, then it would be futile to move DFO forward to Phase III evaluation.
- To assess the safety of DFO infusions (32 mg/kg/day, up to a maximum daily dose of 6000 mg/day), given for 3 consecutive days, in a large cohort of ICH patients. We specifically wish to collect more data on treatment-related adverse events in order to ascertain that patients with ICH can complete this dose given over 3-day duration of infusion without experiencing unreasonable neurological complications, increased mortality, or other serious adverse events related to DFO use, in particular adult respiratory distress syndrome (ARDS).

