STUDY STATUS AND SAFETY RESULTS - Throughout the study, we continued to assess the safety of DFO. Enrollment was placed on hold after enrollment of 42 subjects to investigate a potential safety concern – Adult Respiratory Distress Syndrome (ARDS). ARDS is reported as a potential side effect of prolonged intravenous infusions of high dose DFO in the product's package insert. Five cases of ARDS were reported. An expert in ARDS, blinded to treatment assignments, reviewed all 5 cases as well as 3 cases reported as respiratory failure and 3 cases reported as pulmonary edema. The expert concluded that 2/3 cases reported as pulmonary edema were possibly/probably ARDS, suggesting a total of 7 ARDS cases. The expert review identified a plausible cause for ARDS, other than the study drug or ICH itself, in 4 cases, while no other explanation was apparent for the remaining 3 cases. After careful review of the data, the DSMB unblinded the investigators to the treatment assignment. Six of the 7 cases of ARDS occurred in the DFO-treated group. Three of the 42 enrolled subjects died (7%); all had ARDS, and the cause of death was attributed to ARDS in 2 subjects. No other safety concerns emerged. A total of 36 SAEs were reported in 15 subjects; 22 of which occurred in 9 DFO-treated subjects. One MedWatch report was submitted for hypophosphatemia as it was judged to be severe, unexpected, and possibly related to the study drug. Overall, hypophosphatemia was reported as an AE in 3 subjects (2 in the DFO- and 1 in the placebo group). Other analyses are yet to be performed.

CONCLUSIONS - The NINDS-appointed DSMB concluded that: "although the ARDS cases in the treatment group were in the ballpark frequency of at least one paper in the literature on ARDS in patients with ICH [Elmer 2013], the imbalance in the frequency of ARDS cases between the treatment and placebo groups suggested that pulmonary toxicity of the

drug was highly likely". HI-DEF was therefore terminated due to safety concerns, and the initial protocol has been modified to minimize the potential for pulmonary toxicity of DFO and to enhance the safety of future participants.

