Reporting of respiratory compromise, as well as any serious or life-threatening adverse event, will trigger notification of the event to the Project Manager (PM), the independent MSMs, and appropriate members of the Executive Committee (EC). The MSMs will conduct an independent review of each of these events to determine its relatedness to the study drug along with other elements, and to confirm or exclude the diagnosis of ARDS in cases of respiratory compromise. Within 72 hours of receipt of these events for review, the MSMs will enter into the trial's database their opinion regarding whether the adverse event is, in fact, serious, and if it is unexpected and related to the study drug. If the MSMs believe all three elements are present in the SAE, an expedited safety report (MedWatch) will be filed with the FDA within the stipulated regulatory guidelines: for fatal or life-threatening SAEs, no later than 7 calendar days after the sponsor's initial receipt of information, and for SAEs outside those categories, no later than 15 calendar days after the sponsor determines that the event requires expedited reporting (21 CFR 312.32(c)(1)). If the study site investigator(s) and the MSMs are not in agreement on these issues and fail to resolve their disagreement after direct communication, the opinion of the MSMs will be considered as the final adjudication. When a MedWatch Report is filed with the FDA, a copy of the MedWatch Report (or a link to a secure file in the trial database) will be sent to the DSMB through the NINDS liaison.

Each clinical site PI and primary Study Coordinator will receive an email notification that a MedWatch Report has been filed with FDA. The email notification will contain instructions for accessing the report. It is the responsibility of each clinical site PI to file these reports with his/her IRB in compliance with their institution's local requirements. After the submission of the initial MedWatch Report, the principal investigator at the corresponding clinical site will be responsible for obtaining follow-up information about the event and reporting it in the WebDCU™.

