7.7 STOPPING RULE

The occurrence of ARDS will be continuously monitored during the course of the trial, in order to facilitate thorough review of the data by the DSMB and to stop enrollment into the trial if sufficient evidence of imbalance in the rate of ARDS exists. The NINDS-appointed DSMB recommended that recruitment be stopped if the difference in the number of confirmed ARDS cases between the groups is 5 at any time during the recruitment of the first 40 subjects; 10 at any time during the recruitment of subjects 41-80; 12 at any time during the recruitment of patients 81-120; or if the difference in the number of confirmed ARDS cases between the groups is statistically significant after 40, 80, or 120 subjects have completed the in-hospital phase based on a Pocock-adjusted, one-sided, 0.05 alpha level. This one-sided hypothesis is consistent with our concern for patient safety, wherein early termination is considered only if ARDS incidence is higher on the DFO arm than on the control arm.

These analyses will be based on the occurrence of confirmed ARDS cases (according to the Berlin criteria) thought to be at least possibly related to study drug. The ARDS cases will be reviewed on an ongoing basis throughout the trial by the MSMs (who will adjudicate all cases together to provide a consensus opinion about the diagnosis, severity, and possible plausible causes other than the study drug). The DSMB will be notified of each individual ARDS occurrence upon confirmation by the MSMs, per their request. Given that a common definition for the diagnosis of ARDS will be used, we do not anticipate much discrepancy between the site's assessment and the MSM's assessment. However, in the event of disagreement, the MSM's assessment will be used.

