As secondary analyses of the primary outcome, the presence of a differential treatment effect in the OTT windows will be explored. The generalized linear model described above for the primary analysis will be expanded to include an interaction between treatment and OTT window. While the Trial will be underpowered to definitively address this question, the magnitude of the treatment effect, and corresponding confidence interval, will be estimated for each time window. A dichotomized analysis considering the proportion of DFO- and placebo-treated subjects with mRS 0-3 will also be performed. Although mRS 0-3 is less favorable than the primary outcome of mRS 0-2, it would still be a desirable effect in patients with ICH given that no treatments exist to reduce disability. The trial is adequately powered to assess the futility hypothesis using mRS 0-3 as the outcome based on an absolute difference in treatment effect <13% in favor of DFO. We will also perform similar analyses at 180 days and ordinal analysis across all mRS scores as secondary outcome measures.

8.2.2 SAFETY ENDPOINTS:

All adverse events will be assessed until day-7 or discharge (whichever is earlier), and SAEs until day-90. Mortality (all causes and ICH-related) will be assessed until the end of the study (day-180). Safety endpoints of particular interest include all DFO-related adverse events until day-7 or discharge (whichever is earlier), all SAEs through day-90, and deaths (all causes and ICH-related) through day-180.

The following events will be defined as **ADVERSE EVENTS OF SPECIAL INTEREST** (AEOSI) for safety surveillance during this study: 1) Anaphylaxis (at any time point during study drug infusion); 2) Hypotension (defined as a decrease in blood pressure requiring medical intervention at any time point during drug infusion that cannot be explained by other causes); 3) Respiratory compromise of any cause during the in-hospital phase (day-7 or discharge, whichever is earlier); and 4) Development of new and unexplained visual or auditory changes after initiating treatment with the study drug.

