All adverse events or complications will be submitted electronically via the WebDCU™ system and assigned to a system-organ class and preferred term using MedDRA coding dictionary. The number and percent of all adverse events will be summarized for each treatment arm by event type. Tables will be generated to detect any clinically significant laboratory abnormalities in change of values from baseline to end of the last infusion. We anticipate no missing safety data regarding adverse events, since patients will remain hospitalized and closely monitored until day-7 or discharge (whichever is earlier). The cumulative incidences of each AEOSI, as well as mortality, will be compared via 95% confidence intervals. Mortality will also be assessed via the log rank test for comparing survival curves.

Analysis of the safety data regarding the occurrence of ARDS will be carried out continuously throughout the trial by the unblinded study statistician, who will notify the EC and DSMB if recruitment must be stopped. The DSMB will be notified of each individual ARDS occurrence upon confirmation by the MSMs, per their request. Analysis of other safety data by the DSMB will occur semiannually (or more frequently if requested by the DSMB). If any of these analyses reveal serious emerging concerns, the EC, in consultation with the DSMB, may implement modifications to assure safety as necessary. Apparent, consistent and persistent evidence of net harm that tends to overwhelm any benefit may allow for premature termination of the study.

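### ARDS, the event named in the second primary objective, is formally compared between arms only in the stopping rule; the end-of-trial safety comparison uses any-cause respiratory compromise, and the protocol is inconsistent on whether ARDS is an AEOSI

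*Protocol*

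**What the plan says.** - **Objective.** Protocol 1.1 sets out to show that patients can complete the regimen "without experiencing unreasonable neurological complications, increased mortality, or other serious adverse events related to DFO use, in particular adult respiratory distress syndrome (ARDS"). The synopsis and section 3.1 also name ARDS.
- **Final comparison.** Section 8.2.2 lists four AEOSI: anaphylaxis, hypotension, respiratory compromise, and visual or auditory change. The respiratory item reads "Respiratory compromise of any cause during the in-hospital phase (day-7 or discharge, whichever is earlier"). The rule for analysis is: "The cumulative incidences of each AEOSI, as well as mortality, will be compared via 95% confidence intervals". Other events are covered by "The number and percent of all adverse events will be summarized for each treatment arm by event type".
- **AEOSI list elsewhere.** Section 10.4, on the DSMB review, treats ARDS as one of the AEOSI. The list in 8.2.2 does not name it.
- **Stopping rule.** Section 7.7 does compare ARDS between arms. Recruitment stops if the case difference reaches 5 within the first 40 subjects, 10 within subjects 41 to 80, or 12 within subjects 81 to 120, or if it is "statistically significant after 40, 80, or 120 subjects have completed the in-hospital phase based on a Pocock-adjusted, one-sided, 0.05 alpha level". Cases must meet the Berlin criteria and be thought at least possibly related to study drug.
- **Adjudication.** Under 7.5 the independent Medical Safety Monitors (MSMs) review every case of respiratory compromise "to confirm or exclude the diagnosis of ARDS in cases of respiratory compromise".

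**The concern.** HI-DEF was terminated because ARDS was unevenly split between the arms, and the present trial lowered dose and duration in response. Its safety report should therefore estimate the ARDS risk on the new regimen directly. Instead, the protocol assigns its final interval to a broader event, which also takes in respiratory failure and pulmonary edema that are not ARDS. If those other events occur equally in both arms, they leave the absolute difference unchanged, widen its interval and pull the risk ratio towards 1. A moderate ARDS excess could then be reported as no clear difference in respiratory compromise.

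The by-arm event table is only partial cover. It is built from submitted, MedDRA-coded events and carries no stated interval, and 8.2.2 does not say whether the MSM diagnosis or the site term is tabulated. In this programme the two have differed. In HI-DEF, "The expert concluded that 2/3 cases reported as pulmonary edema were possibly/probably ARDS", so 2 of the 7 ARDS cases had been reported under another term. One of two phase I respiratory failures was also later judged to be undiagnosed ARDS.

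**Working it through.** **1. The protocol's own sample size, to fix the analysis n.** Section 8.4 gives 28% good outcome in both arms, margin 0.12, one-sided alpha 0.10 and power 80%.

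n per arm = 2(0.28)(0.72)(1.2816 + 0.8416)² / 0.12² = 126.2, rounded up to 127; total 254. Then 254 × 1.11 = 281.9, rounded up to 282; 282 × 1.04 = 293.3, rounded up to 294. The stated figures reproduce. Removing the factor for subjects never treated leaves 294 / 1.04 / 2 = 141 treated per arm. The protocol states no sample size or power for any ARDS or respiratory comparison.

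**2. Reach of the formal ARDS tests.** The last limit and the last test fall at 120 subjects: 120 / 294 = 41%. The other 174 enter no named ARDS comparison. A Pocock boundary for three equally spaced looks at one-sided 0.05 has a constant of about 1.99 (nominal p about 0.023). It is a rule for halting recruitment and yields no end-of-trial estimate.

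**3. Sensitivity of the two endpoints.** The protocol gives no ARDS or background respiratory rate for this trial, so the following rates are assumptions. Let ARDS occur in p0 (placebo) and p1 (DFO), and let other respiratory compromise add q to each arm. With a = p0 + q and b = p1 + q:

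SE = √[a(1−a)/141 + b(1−b)/141]; chance that the 95% CI excludes zero = Φ((b−a)/SE − 1.96).

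| ARDS, DFO v placebo | q | Rates compared | Risk ratio | SE | Chance CI excludes 0 |
|---|---|---|---|---|---|
| 8% v 2% | 0 (ARDS alone) | 8% v 2% | 4.00 | 0.0257 | 0.65 |
| | 10% | 18% v 12% | 1.50 | 0.0424 | 0.29 |
| | 20% | 28% v 22% | 1.27 | 0.0514 | 0.21 |
| | 30% | 38% v 32% | 1.19 | 0.0567 | 0.18 |
| 6% v 1% | 0 (ARDS alone) | 6% v 1% | 6.00 | 0.0217 | 0.64 |
| | 10% | 16% v 11% | 1.45 | 0.0406 | 0.23 |
| | 30% | 36% v 31% | 1.16 | 0.0561 | 0.14 |

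**4. Small counts.** At 2% the placebo arm expects 141 × 0.02 = 2.8 cases, where the normal approximation is rough. Enumerating all outcomes for 8% v 2% with Fisher's two-sided test at 0.05 gives 0.55 for ARDS alone, and 0.24, 0.18 and 0.15 with q of 10%, 20% and 30%. The level is lower, but the relative loss is similar.

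**5. HI-DEF rates.** With 6/21 (section 3.3) against 1/21 (7 cases among 42 subjects, 6 of them on DFO), the chance is essentially 1 for ARDS alone and stays at or above 0.98 for q up to 30%. The loss therefore concerns moderate excesses.

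**6. Are non-ARDS events a realistic addition?** In HI-DEF (2.2.3) the expert reviewed 5 + 3 + 3 = 11 respiratory cases and judged 7 to be ARDS, leaving 4 that were not. Their arms are not stated. For ARDS alone, 6/21 v 1/21 gives one-sided Fisher p = 0.047. For all 11 cases, an even split of the 4 gives 8/21 v 3/21, p = 0.079. The range is 0.50 if all 4 were on placebo to 0.002 if all 4 were on DFO. The composite can therefore lose or gain, depending on where the other events fall.

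**The case against.** A reader might infer that ARDS is never compared between the arms. The protocol does not support that. Section 7.7 gives ARDS its own between-arm limits and tests on adjudicated cases, and 8.2.2, 9.3 and 10.4 have the unblinded statistician monitor it continuously. What remains true is that no limit or test is stated beyond subject 120, that the relatedness filter applies, and that all of this serves the decision to stop recruitment.

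A reader might also infer that the safety objective would go unanswered. That goes too far. SAEs are collected to day 90 and events are tabulated by arm, so serious ARDS should appear, and an interval can be worked out from reported counts.

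Nor is the day-7 closure of the respiratory item the cause of the problem. In HI-DEF, mean onset among the DFO cases was about 78 hours (section 3.3).

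The misreporting seen in HI-DEF may not recur at the same rate. The present protocol requires Berlin criteria, daily oxygenation checks in intubated patients, 24-hour reporting of respiratory compromise and MSM review. Under 7.7 the MSM opinion prevails over that of the site, although that sentence sits in the stopping-rule section.

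An any-cause respiratory item is a sound surveillance net, because that is how disguised ARDS cases are found. This stands, and it is a reason to keep the item alongside ARDS.

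Finally, section 10.4 could be read as treating ARDS as one form of respiratory compromise, and a separate SAP, not available here, may already add an ARDS line. Both are possible. Even so, the protocol itself fixes the AEOSI list and the comparison, and its two statements should agree.

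**Conclusion.** The point holds in limited form. The protocol's final interval comparison is set on a broader event than its second primary objective names, and 8.2.2 and 10.4 do not match. The formal ARDS comparison stops at 41% of planned enrolment and excludes cases judged unrelated to drug.

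The size depends on rates the protocol does not give. With 141 treated per arm, ARDS at 8% v 2% and equal other respiratory events of 10% to 30%, the chance of an interval excluding zero falls from about 65% to between 29% and 18%. At HI-DEF rates the loss is negligible, and it shrinks or reverses if DFO also raises other respiratory events. A moderate excess is nevertheless a plausible case to plan for, because dose and duration were cut to reduce ARDS. The change is worth making because it answers the stated objective more directly at almost no cost; nothing here shows that the trial's safety data are inadequate.

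**What to change.** - Reconcile the AEOSI list in 8.2.2 (and the synopsis) with the wording in 10.4, so that the protocol says once whether ARDS is an AEOSI.
- In 8.2.2, add MSM-confirmed ARDS by the Berlin criteria, regardless of judged relatedness, as its own line in the final by-arm comparison over all treated (mITT) subjects. Report the risk difference with a 95% CI, preferably by an exact or score method because counts will be small. Make this the main respiratory result for the second primary objective.
- Keep any-cause respiratory compromise as a supporting AEOSI.

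The stopping rule in 7.7 need not change for this. The cost is a wording change and one more table line. The MSM adjudications are already required, so no new data, staff, visits or patients are needed.

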6.1.1 CLINICAL AND LABORATORY ASSESSMENTS

The following assessments will be carried out throughout the 90-day study period:

Upon screening of potential study subjects: 1) Review of head CT and determination of the time of ICH onset or the time the patient was last known to be without presenting deficits; 2) Demographic data; 3) Medical history; 4) Review of medications; 5) General physical examination; 6) Neurological examination, including NIHSS and GCS; 7) Visual and auditory assessment (which includes assessments for cataracts, visual loss or field cut, disturbed color vision, hearing loss, and presence of tinnitus), whenever possible in awake patients; 8) Determination of pre-morbid mRS; 9) Review of admission laboratory tests - Hematology [hemoglobin, hematocrit, red blood cell count and platelet count]; Coagulation [partial thromboplastin time and international normalized ratio]; and serum albumin; and 10) Review of all inclusion/exclusion criteria. A baseline chest x-ray is required to rule out the presence of bilateral pulmonary infiltrates or pulmonary edema. A pregnancy test is required for all women of childbearing potential prior to enrollment into the study. Subjects in whom all eligibility criteria are met should be considered for enrollment, and those who agree to participate via signed and dated informed consent should be enrolled.

Participants should be reassessed immediately prior to the study drug administration to obtain a pre-treatment baseline. **The Pre-treatment baseline reassessments include:** 1) Vital signs, including blood pressure and heart rate; 2)

Neurological examination, including NIHSS and GCS to confirm stability of their neurological status and to obtain pre-treatment baseline scores; and 3) Assessment for new adverse events since screening. Patients who exhibit significant clinical or neurological deterioration (i.e. develop fixed dilated pupils or GCS decreases to ≤ 6) prior to administration of the first dose of the study drug should not receive the study drug, and their participation will be terminated.

Administration of the study drug should only be permitted after obtaining pre-treatment blood sample for serum chemistry and glucose, hepatic function tests, and urine analysis (if not already done upon arrival to the ED).

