Subjects who receive the study drug(s) will be evaluated daily for the first 3 days (during study drug infusion while in hospital) and on day-7 or discharge from the hospital, whichever occurs first. Clinic visits will take place on days 30 ± 7 and 90 ± 7 . Telephone interviews will be conducted on day 60 ± 7 and 180 ± 7 .

The following assessments should be performed **after each daily infusion** (every 24 ± 6 h) and through the day following completion of the last infusion: 1) General physical examination; 2) Visual and auditory assessments; 3) Neurological examination, including NIHSS and GCS; and 4) Vital signs, including blood pressure and heart rate. A repeat head CT scan and blood samples for hematology, serum chemistry, renal and hepatic function tests, coagulation studies, and urine analysis should be obtained within 24 ± 6 h following the last infusion of the study drug. Vital signs (blood pressure and pulse) and neurological functions should be assessed at least once every 4h during intravenous drug infusions. Daily urinary output checks should be carried out every day until the day following the last infusion. In addition, the following data must be checked at least once daily for all intubated patients (or more frequently in patients with changes in respiratory status requiring changes in ventilator settings and increased oxygen requirement) throughout day-7 or discharge and entered into Web-DCU™: 1) $\text{PaO}_2/\text{FiO}_2$ ratio; 2) Plateau and peak pressures; and 3) Chest X-ray results (when available). **A chest x-ray is required if the $\text{PaO}_2/\text{FiO}_2$ ratio is < 300 .**

On day-7 or Discharge (whichever comes first), the following assessments are done: mRS, NIHSS, GCS, MoCA and visual and auditory assessments.

During hospitalization, the NIHSS and GCS should be done any time a subject's neurological status deteriorates, or whenever the investigator believes it is prudent to do an assessment. Laboratory assessments beyond those required for the study should be done whenever clinically indicated.

The **Day-30 (± 7)** will be an in-person visit comprised of a general physical examination, visual and auditory assessments, review of SAEs, and assessments of NIHSS, SIS-16, MoCA and mRS.

The **Day-60 (± 7)** assessments, which will be completed via telephone, will be comprised of a functional assessment to obtain a score on mRS and query for SAEs.

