The **Day-90 (± 7)** visit will be an in-person visit comprised of a general physical examination, visual and auditory assessments, and assessments of NIHSS, MoCA, SIS-16, and mRS. However, a telephone interview to obtain a score on mRS (the primary outcome measure) may be allowed on a case-by-case basis, after consultation with the PI, if the subject is unable to return for an in-person evaluation.

The **Day-180 (± 7)** assessments, which will be completed via telephone, will be comprised of a functional assessment to obtain a score on mRS.

A study staff member certified in NIHSS and mRS and experienced in administering GCS, SIS-16, and MoCA should perform the assessments at all time points. We require that all assessments at all time points be performed by the same blinded

investigator, whenever possible, to minimize inter-rater variability. Data on the subject’s functional status (mRS and SIS-16) can be obtained from a proxy if the subject is unable to provide the information. Please refer to Appendix V for details of NIHSS, GCS, SIS-16, and MoCA scales.

Concomitant medications and non-drug therapies should be assessed at all points of contact with the subject after study drug initiation. All adverse events (serious and non-serious) should be assessed until day-7 or discharge, whichever occurs first. All new SAEs will be monitored until day-90, resolution of the SAE, or withdrawal of consent, whichever is earlier. Continuing SAEs beyond day-90 will be monitored until day-180.

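### The visual/auditory event of special interest has no end date and is examined after day 7, but the text gives non-serious changes found then no reporting route, and Table 6.2 does not agree with the text

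*Protocol*

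**What the plan says.** **Definition.** Section 8.2.2 lists four adverse events of special interest (AEOSI). Anaphylaxis and hypotension count only during the infusion, and respiratory compromise only in the in-hospital phase. The fourth is "Development of new and unexplained visual or auditory changes after initiating treatment with the study drug", with a start and no end. The synopsis defines it in the same open way.

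**Examination.** Section 6.1.1 describes a visual and auditory assessment that covers, among other things, visual loss, field cuts, hearing loss and tinnitus. It is made "whenever possible in awake patients". It is repeated during treatment and at day 7 or discharge. The day-30 visit consists of "general physical examination, visual and auditory assessments, review of SAEs, and assessments of NIHSS, SIS-16, MoCA and mRS". The section 6.1.1 text also requires the assessment at day 90.

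**Collection.** Section 6.1.1 says "All adverse events (serious and non-serious) should be assessed until day-7 or discharge, whichever occurs first", and section 8.2.2 says "All adverse events will be assessed until day-7 or discharge (whichever is earlier), and SAEs until day-90". The synopsis and sections 3.2, 5.2 and 7.1 give the same limit.

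**Analysis.** Section 8.2.2 says "The cumulative incidences of each AEOSI, as well as mortality, will be compared via 95% confidence intervals". No time horizon is given.

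**The concern.** The open definition and the later examinations suggest that the plan wants to know about sensory changes beyond the hospital stay. The collection rule in the text does not follow. New tinnitus or mild hearing loss first noted at day 30 meets the AEOSI definition, but if it is not serious, a site that follows the text has no adverse event report to file.

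Safety is the second primary objective, and section 2.1.3.2 lists ocular and auditory disturbances among the drug's reported reactions. Because the assessment depends on the patient being awake, and eligibility admits a GCS just above 6, day 30 could be the first usable examination after treatment for some subjects.

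The SAP cannot fully repair this. What sites must report, and until when, is set by the protocol.

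**Working it through.** The plan states no figure on this point, so the check sets its provisions side by side. The columns for section 6.1.1 and Table 6.2 show where they agree and where they do not.

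| Time | Visual/auditory exam, 6.1.1 | Visual/auditory exam, Table 6.2 | Event collection, text | Adverse Events row, Table 6.2 |
|---|---|---|---|---|
| 24 h to day after last infusion | yes | ticked | all events | ticked |
| Day 7 or discharge | yes | ticked | all events, last time | ticked |
| Day 30 | yes | ticked | SAEs only | ticked |
| Day 60 (phone) | no | not ticked | SAEs only | ticked |
| Day 90 | yes | **not ticked** | SAEs only | ticked |
| Day 180 (phone) | no | not ticked | continuing SAEs and deaths | not ticked |

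1. *Does the AEOSI definition close at day 7?* No. Section 8.2.2 closes the respiratory item at day 7 or discharge and leaves the visual/auditory item open in the same list.

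2. *Is this AEOSI exempted from the day-7 limit?* No. None of the places that state the limit makes an exception for it.

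3. *Does Table 6.2 settle the matter?* No. Its Adverse Events row runs to day 90 without a restriction to SAEs. There is no separate SAE row, and the text repeats the limit several times, so the later ticks most likely mean SAEs. That is an inference. If they mean all events, the table contradicts the text.

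4. *Is the day-90 examination certain?* No. Section 6.1.1 requires it and Table 6.2 does not tick it. The Physical Examination row of the same table does have its day-90 tick.

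5. *What is still captured late?* Anything meeting a seriousness criterion in section 7.1, such as significant disability, is collected to day 90. The gap is limited to non-serious changes.

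6. *How long is the uncovered period?* Non-serious collection lasts at most 7 days. That is 7/30 = 23% of the time to the day-30 examination, or 7/90 = 7.8% of the time to the day-90 one, and less with early discharge. These are shares of calendar time, not of events.

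7. *Can the loss be sized?* Let p be the true incidence in an arm and f the fraction of its cases that are non-serious and first found after day 7 or discharge. Under the text rule the reported incidence is p × (1 − f). The documents give neither p nor f, so no value follows.

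8. *Do other passages assume the short window?* Section 8.2.2 expects no missing adverse event data because patients are in hospital until day 7 or discharge. That reason does not cover an event with no end date. Section 10.4 describes AEOSI review from treatment start to day 7 or discharge, but in connection with the first DSMB meeting, after 40 subjects. It does not fix the horizon of the final analysis.

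**The case against.** The strongest reply is that this is an ambiguity rather than a demonstrated loss.

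- **Specific over general.** An open AEOSI definition could be read as an exception to the general window, and the Adverse Events ticks through day 90 fit that reading. It is possible, but nothing in the text says so, and the day-30 visit names only SAEs. A site following the text would not report the event.
- **The findings may survive as examination data.** The assessment is a row of the data collection schedule, so a change from screening might be derived later. This stands. The plan does not say, however, that such findings count toward the AEOSI.
- **Late onset is not expected.** Section 2.1.3.2 ties these disturbances to prolonged, high-dose use in patients with low ferritin and says most were reversible. Here treatment lasts 3 days, and Table 6.2 has five assessments from 24 h through day 7. This stands too, and the number of late cases may be small.

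A reader might go further and infer that no late case can be captured and that the comparison is biased toward no drug effect. The documents support neither. Serious changes are captured to day 90, and the Table 6.2 row leaves the rest unclear. The cut-off applies to both arms. From the expression above, if f is equal in the two arms the risk difference shrinks by the factor (1 − f) while the risk ratio is unchanged; if f differs, the direction depends on values that are not given.

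**Conclusion.** The point holds as an inconsistency in the collection window of one named safety endpoint. By the text, a non-serious visual or auditory change first found after day 7 or discharge fits the AEOSI definition but has no adverse event reporting route, so the between-arm cumulative incidence may omit it. Table 6.2 disagrees with the text twice: on adverse events after day 7, if its row means all events, and on the day-90 visual/auditory assessment.

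The conclusion rests on reading the repeated day-7 limit literally and on the table's columns having been read correctly from the PDF. Its size cannot be stated, because the documents give neither an incidence nor a share of late findings. It does not touch the primary futility analysis. It is worth correcting because the examinations are already scheduled and the change is cheap.

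**What to change.** - In sections 6.1.1, 7.1 and 8.2.2, require any new, unexplained visual or auditory change to be reported as an AEOSI, serious or not, through the last scheduled visual/auditory assessment. Carry the exception into the synopsis and sections 3.2 and 5.2, which repeat the general limit.
- In section 8.2.2, state that same horizon for the cumulative incidence of this event.
- Add the event to the day-30 review, and to the day-90 review if that assessment is kept.
- Reconcile Table 6.2 with section 6.1.1: decide whether the visual/auditory assessment takes place at day 90, and say what the Adverse Events row means after day 7.
- Align the AEOSI review wording in section 10.4.

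A second consistent choice would be to limit this AEOSI expressly to day 7 or discharge and tabulate later examination findings separately. It would leave those findings out of the AEOSI comparison.

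The cost is wording and one more reportable event type at visits that already include the examination. The downside is a few more event forms in both arms, some for changes unrelated to the drug.
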